4.2 Inclusion criteria

Patients must meet ALL the following inclusion criteria to be eligible for enrolment into the study:

1. Signed Informed Consent Form (ICF) prior to beginning specific protocol procedures.
2. Aged ≥ 18 years at time of signing ICF.
3. Eastern Cooperative Oncology Group (ECOG) performance status of 0-1.

4. Women in a well-determined premenopausal status as indicated in the protocol Section 4.1.
5. Histologically confirmed invasive breast carcinoma, with all the following characteristics:
 - a. Documented ER-positive tumor in accordance with American Society of Clinical Oncology (ASCO)/College of American Pathologists (CAP) guidelines (Allison et al., 2020), assessed locally and defined as $\geq 1\%$ of tumor cells stained positive.
 - b. Documented HER2-negative tumor in accordance with 2018 ASCO/CAP guidelines (Wolff et al., 2018), assessed locally at baseline.

Note: Diagnostic biopsy taken no more than 8 weeks prior to initiation of study treatment can be used as baseline.

- c. Ki67 score $\geq 10\%$ analyzed locally and centrally confirmed (Nielsen et al., 2021).

Note: Ki67 will be analyzed locally at the time of inclusion. Patients with basal Ki67 $\geq 20\%$ will be assessed locally and centrally confirmed retrospectively and patients with 10-19% will be assessed centrally before inclusion.

- d. Tumor size must be ≥ 1.0 cm in longest diameter by ultrasound as per Response Evaluation Criteria in solid Tumors (RECIST) criteria.

Note: Patients with multifocal or multicentric breast cancer with a at least one tumor lesion ≥ 1.0 cm in the longest diameter by ultrasound (reference lesion) are also eligible if the two largest lesions have been histologically confirmed in the clinical evaluation and meet pathologic criteria for ER positivity and HER2 negativity.

6. Willingness to provide a primary tumor tissue and blood sample obtained at baseline as well as a post-treatment tumor tissue and blood samples (breast biopsy or from breast surgery).
7. Patient has adequate bone marrow, liver, and renal function:
 - Hematological: absolute neutrophil count (ANC) $\geq 1.5 \times 10^9/L$ (1500/mL), platelet count $\geq 100.0 \times 10^9/L$, and hemoglobin ≥ 9 g/dL (≥ 90 g/L).

Note: The blood counts are to meet the specified criteria without transfusion or growth factor support, unless it is clear that the bone marrow function is adequate and that any aberration has a clear and correctable cause, and the correction undertaken.

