- Hepatic: total serum bilirubin $\leq 1.5 \times$ institutional upper limit of normal (ULN) (patients with known Gilbert's syndrome: $\leq 3 \times$ ULN); alkaline phosphatase (ALP) ≤ 2.5 times ULN; aspartate transaminase (AST) and serum alanine transaminase (ALT) $\leq 3 \times$ times ULN.

- Coagulation: The international normalized ratio (INR) < 1.5' ULN and partial thromboplastin time (PTT or aPTT) < 1.5' ULN (except for patients receiving anticoagulation therapy). For patients receiving warfarin, a stable INR between 2 and 3 is required. For patients receiving heparin, PTT (or aPTT) between 1.5 and 2.5' ULN (or patient value before starting heparin treatment) is required. If anticoagulation therapy is required for a prosthetic heart valve, stable INR between 2.5 and 3.5 is permitted.
 - Renal: creatinine clearance ≥ 60 mL/min for patients with creatinine levels above institutional normal.
8. Negative serum pregnancy test result within 14 days prior to initiation of study treatment and a negative urine pregnancy test within 24 hours prior to study treatment initiation.

Note: Premenopausal women age ≥ 18 years with premenopausal status defined as: estradiol (E2) in the premenopausal range (according to institution parameters) or patient has been menstruating regularly during the 6 months prior to randomization and has not used any form of hormonal contraception or any other hormonal treatments during this time.

Women must remain abstinent and truly abstains from sexual activity (refrains from heterosexual intercourse) or use of locally recognized adequate methods of contraception (described as that with a failure rate <1%) during the length of the study, and to continue its use for 10 days after the last dose of study treatment (for patients taking giredestrant) or 9 months following cessation of therapy (for patients in the tamoxifen arm). They must, as well, agree to refrain from donating eggs during the same period of time.

Examples of non-hormonal contraceptive method with a failure rate of <1% per year (e.g. bilateral tubal ligation, male sterilization and copper intrauterine devices). The reliability of sexual abstinence should be evaluated in relation to the duration of the clinical trial and the preferred and usual lifestyle of the individual. Periodic abstinence (e.g., calendar, ovulation, symptothermal, or postovulation methods) and withdrawal are not adequate methods of contraception.

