 - History of documented congestive heart failure (New York Heart Association Class II-IV) or cardiomyopathy.
 - QT interval corrected through use of Fridericia's formula (QTcF) >470 ms by at least three ECGs >30 minutes apart.
 - History of long or short QT syndrome, Brugada syndrome or known history of corrected QT interval prolongation, or torsades de pointes.

- History or presence of an abnormal ECG that is clinically significant in the investigator's opinion.
 - History of ventricular dysrhythmias or risk factors for ventricular dysrhythmias such as structural heart disease (e.g., severe left ventricular systolic dysfunction, left ventricular hypertrophic cardiomyopathy, infiltrative cardiomyopathy, moderate-to-severe valve disease), coronary heart disease (symptomatic or with ischemia demonstrated by diagnostic testing), clinically significant electrolyte abnormalities (e.g., hypokalemia, hypomagnesemia, hypocalcemia), or family history of long QT syndrome.
11. Any serious medical condition or abnormality in clinical laboratory tests that, in the investigator's judgment, precludes the patient's safe participation in and completion of the study.
 12. Treatment with strong CYP3A4 inhibitors or inducers within 14 days or 5 drug elimination half-lives (whichever is longer) prior to randomization.
 13. Active inflammatory bowel disease or chronic diarrhea, short bowel syndrome, or major upper gastrointestinal surgery including gastric resection.
 14. Participants who have a known allergy or hypersensitivity to any of the study drugs or any of their excipients.
 15. Participants who are pregnant or breastfeeding or intending to become pregnant during the study or within 10 days after the final dose of giredestrant (GDC-9545), or within 9 months after the final dose of tamoxifen.

Note: Women of childbearing potential must have a negative serum pregnancy test result within 14 days prior to initiation of study treatment and a negative urine pregnancy test within 24 hours prior to study treatment initiation.

16. Patients with renal dysfunction who require dialysis.
17. Participants who have had a serious infection requiring oral or IV antibiotics within 14 days prior to screening or other clinically significant infection (e.g., COVID-19) within 14 days prior to screening.

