6.5.2 Pregnancy and assessment of fertility

Premenopausal status is defined as estradiol (E2) in the premenopausal range (according to institution parameters) or patient has been menstruating regularly during the 6 months prior to randomization and has not used any form of hormonal contraception or any other hormonal treatments during this time.

All patients must undergo a serum pregnancy test at screening to confirm eligibility in the trial and within 14 days prior to initiation of study treatment (with result available prior to dosing), and a urine pregnancy test (with results available prior to dosing) within 24 hours prior to study treatment initiation.

All patients must remain abstinent and truly abstains from sexual activity (refrains from heterosexual intercourse) or use of locally recognized adequate methods of contraception (described as that with a failure rate $< 1\%$) during the length of the study, and to continue its use for 10 days after the last dose of study treatment (for patients taking giredestrant) or 60 days

following cessation of therapy (for patients in the tamoxifen arm). They must, as well, agree to refrain from donating eggs during the same period.

Examples of non-hormonal contraceptive method with a failure rate of <1% per year are bilateral tubal ligation, male sterilization and copper intrauterine devices.

The reliability of sexual abstinence should be evaluated in relation to the duration of the clinical trial and the preferred and usual lifestyle of the individual. Periodic abstinence (e.g., calendar, ovulation, symptothermal, or post ovulation methods) and withdrawal are not adequate methods of contraception.

An additional pregnancy test is indicated in the EoT visit and in the EoS visit, when a urine pregnancy test should be performed.

In case of pregnancy during study treatment or within 10 days after the last dose of study treatment (for patients taking giredestrant) or 60 days following cessation of therapy (for patients in the tamoxifen arm), the patient must permanently stop study treatment immediately and/or withdraw from the trial, and the pregnancy must be reported on the Clinical Trial Pregnancy Form as specified in **Section 7.2.4**.

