7.2.4 Pregnancy reporting

Irrespective of the treatment received by the subject/patient, any subject/patient's or subject/patient's partner pregnancy occurring during study treatment or within 10 days after the

last dose of study treatment (for patients taking giredestrant) or 60 days following cessation of therapy (for patients in the tamoxifen arm) must be reported within 24 hours of investigator's knowledge of the event.

Patients will be instructed to immediately inform the investigator if they become pregnant during the study or within 28 days after the final dose of study drug.

Pregnancies will be treated as SAEs and the investigator will complete a Clinical Trial Pregnancy Reporting Form and forward it to the Sponsor according to the reporting instructions provided by MEDSIR at the site initiation visit and filed in the Investigator's File. The investigator should discontinue study drug and counsel the patient, discussing the risks of the pregnancy and the possible effects on the fetus. Monitoring of the patient should continue until conclusion of the pregnancy. Any serious adverse events associated with the pregnancy (e.g., an event in the fetus, an event in the mother during or after the pregnancy, or a congenital anomaly/birth defect in the child) should be reported on the Adverse Event eCRF.

The subject/patient will be asked to provide follow-up information on the outcome of the pregnancy, including premature termination should the case arise and on the infant until 12 months of life. Spontaneous miscarriage and congenital abnormalities will also be reported as SAEs. Follow-up queries may be sent, asking for further information, if required for a comprehensive assessment of the case.

The follow-up period will be deemed to have ended when the health status of the child has been determined at 12 months of the infant's life.

Additional follow-up information on any IMP -exposed pregnancy and infant will be requested at specific time points (i.e., after having received the initial report, at the end of the second trimester, two weeks after the expected date of delivery, and at 3, 6, and 12 months of the infant's life).

A spontaneous abortion should be classified as a serious adverse event (as the Sponsor considers abortions to be medically significant), recorded on the Adverse Event eCRF, and reported to the Sponsor immediately (i.e., no more than 24 hours after learning of the event).

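### For the tamoxifen arm, Protocol 6.5.2 sets contraception and the egg-donation restriction at 60 days after treatment, while inclusion criterion 8 sets 9 months for the same measures

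*Protocol*

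**What the plan says.** Protocol 6.5.2 requires abstinence or adequate contraception during the study and then "to continue its use for 10 days after the last dose of study treatment (for patients taking giredestrant) or 60 days" after therapy for the tamoxifen arm. On egg donation it adds: "They must, as well, agree to refrain from donating eggs during the same period".

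Inclusion criterion 8 in Protocol 4.2 covers the same two measures. Its tamoxifen period is "or 9 months following cessation of therapy (for patients in the tamoxifen arm". The synopsis and SAP 1.3.2 repeat it. Exclusion criterion 15 (synopsis, Protocol 4.3, SAP 1.3.3) bars women who intend to become pregnant during the study "or within 9 months after the final dose of tamoxifen".

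For a pregnancy that occurs, 6.5.2 applies its stop-treatment and reporting sentence up to day 60: "or 60 days following cessation of therapy (for patients in the tamoxifen arm), the patient must permanently stop study treatment immediately". Section 7.2.4 does the same for reporting: "or 60 days following cessation of therapy (for patients in the tamoxifen arm) must be reported within 24 hours". A separate sentence in 7.2.4, common to both arms, has patients told to inform the investigator of a pregnancy that arises while the study lasts or up to 28 days after their final dose.

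The last scheduled pregnancy test is at the end-of-study visit: "An additional pregnancy test is indicated in the EoT visit and in the EoS visit, when a urine pregnancy test should be performed". Section 3.3.4 places that visit 28 days (plus or minus 3) after the last dose and describes it as the final patient visit.

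**The concern.** Every participant is premenopausal, and 46 of the planned 92 are allocated to tamoxifen. The length of the contraception period is therefore a working safety instruction for half the trial, and the protocol gives it two values. Section 6.5.2 is the section on pregnancy and fertility, so site staff may well counsel from it. Staff who did so would give the shorter period and fall out of line with a criterion that every patient had to meet at entry.

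The 7.2.4 mismatch matters because no visit or test is scheduled after the end-of-study visit. From then on the site learns of a pregnancy mainly if the patient says so. An instruction to the patient that stops before the investigator's duty does weakens that duty.

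**Working it through.** **Step 1. The periods side by side.**

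| Place | Subject | Giredestrant | Tamoxifen |
|---|---|---|---|
| Criterion 8: synopsis, Protocol 4.2, SAP 1.3.2 | Contraception, egg donation | 10 days | 9 months |
| Criterion 15: synopsis, Protocol 4.3, SAP 1.3.3 | Intention to become pregnant | 10 days | 9 months |
| Protocol 6.5.2 | Contraception, egg donation | 10 days | 60 days |
| Protocol 6.5.2 and 7.2.4 | Action on, and reporting of, a pregnancy | 10 days | 60 days |
| Protocol 7.2.4 | Patient tells the investigator | Study, or 28 days after last dose | Study, or 28 days after last dose |

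Rows 1 and 3 govern the same measures in the same arm and disagree. The giredestrant value is 10 days in both, so only the tamoxifen figure is out of line. Row 4 has a different subject: the eligibility criteria set no reporting window, so row 4 does not contradict them.

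**Step 2. Size of the contradiction.** Assumption: 9 months = 9 × 30.44 = 274 days (270 to 276 under other conventions).

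- Share covered by 60 days: 60/274 = 21.9% (21.7% to 22.2% over the range).
- Days not covered: 274 − 60 = 214 (210 to 216).

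**Step 3. The mismatch inside 7.2.4.** The patient instruction has two limbs, the study and 28 days after the last dose. The result depends on what the study means.

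- *Individual participation.* This ends at the day-28 visit, so the instruction ends at about day 28. The shortfall against the tamoxifen reporting duty is 60 − 28 = 32 days.
- *The whole trial.* Section 3.3.4 defines the end of study as the last patient's last visit. The synopsis puts it 45 days after the last patient starts treatment. A patient who starts d days before the last patient is then covered until d + 45 days after her own start. Her post-treatment day 60 falls at about 15 + 60 = 75 days after her start. She is covered to day 60 only if d + 45 ≥ 75, that is d ≥ 30. Patients who start in roughly the last 30 days of enrolment fall short. The last one is covered to about 45 − 15 = 30 days after her last dose, about 30 days short of day 60.

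On the trial-wide reading, the instruction reaches 9 months if d + 45 ≥ 15 + 274, that is d ≥ 244 days. With the planned 16-month enrolment (16 × 30.44 = 487 days), that covers patients who start in about the first 487 − 244 = 243 days. The trial-wide reading does not lengthen the investigator's duty, because that window runs from study treatment.

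**Step 4. Contact after the last visit.** The visit falls on day 25 to 31 after the last dose. The part of the 9 months without a planned contact is 274 − 31 = 243 to 274 − 25 = 249 days.

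All these figures describe what the text covers. None is an estimate of risk.

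**The case against.** **The eligibility criteria already protect the patient.** Protocol 4.2 states: "Patients must meet ALL the following inclusion criteria to be eligible for enrolment into the study". Section 6.1.2 has the site complete an eligibility checklist and the medical monitor verify eligibility before inclusion. A site that applies 9 months satisfies both texts. The consent form is not in our copy and may state the right period. This stands, and it lowers the weight of the point. It does not remove it: if criterion 8 is right, 6.5.2 is an error in a section that sites will consult.

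**The reporting window may be shorter by design.** This also stands. Nothing in the documents requires the reporting window to equal the contraception window. A reader might infer that the 60-day reporting periods contradict the 9-month criteria. They do not, because the criteria say nothing about reporting.

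**Late pregnancies may be reportable anyway.** Section 7.2.4 handles pregnancies as SAEs. Section 7.1.1.3 and Appendix 1, note 9, keep treatment-related SAEs reportable after treatment and follow-up, without a stated limit. Section 7.2.4 also puts no time limit on spontaneous abortion, abortion for maternal or embryofetal toxicity, or congenital anomaly. This narrows the gap without closing it: the investigator must learn of the event, and the general late-SAE rule also needs a judgement that it is related. The inference that pregnancies after day 60 simply go unreported is therefore not supported.

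**Conclusion.** The contradiction holds on the current text. For the tamoxifen arm, 6.5.2 gives 60 days where criterion 8 gives 9 months for the same measures. That is a more than fourfold difference (274/60 = 4.6), and no rule says which prevails. It is an internal inconsistency that should be fixed. It does not rank with the gravest findings, because criterion 8 binds at entry and is checked there, the consent wording is unseen and no analysis is touched.

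The secondary point also holds, with its condition. The patient instruction is about 32 days short of the tamoxifen reporting duty if the study means individual participation. If it means the whole trial, patients enrolled in about the last month are still short. A reader might infer that disclosure always ends on day 28 and covers only 28/274 = 10% of the 9 months. That is true only on the first reading, and the text does not settle which is meant.

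Nor do the documents support any statement about fetal risk. Section 1.2 names tamoxifen as standard adjuvant treatment for low-risk premenopausal patients, so some participants may be taking it during these months, and the basis for the 9 months is not given.

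**What to change.** 1. **Correction.** In the 6.5.2 contraception and egg-donation text, replace 60 days with 9 months for tamoxifen. If the sponsor's safety group confirms another single value, use it in every place instead. With 9 months, the synopsis, 4.2, 4.3 and the SAP stay as they are.
2. **Correction.** In 7.2.4, extend the tamoxifen-arm patient instruction to at least the reporting window (60 days now, or longer if item 3 is adopted), and say whether the study means the patient's own participation or the whole trial. The 28 days already exceed the 10-day giredestrant window, so that arm needs no change.
3. **Recommendation, not error correction.** Extend the 60-day windows in 6.5.2 and 7.2.4 to the same 9 months. In 6.5.2 this matters only for the reporting clause, since treatment has ended by day 15 or 16.
4. **Communication.** Once the value is settled, notify sites by the amendment or administrative-letter route in 12.2, and check that the consent form agrees.

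The cost is two to four sentences and the approvals that 12.2 requires for either route (sponsor, global coordinator, site investigators, ethics committees and authorities). Section 12.2 does not let approval hold up immediate safety action, should the sponsor judge that this is needed. A consent-form revision may follow under 9.3. No extra visit is proposed. There is no effect on endpoint, power or analysis, and no SAP change if 9 months is kept.

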6.5.3 Cardiac function monitoring

Cardiac function monitoring consists of a standard 12-lead ECG, and cardiac signs or symptoms collection. All patients must have a standard 12-lead ECG in screening period, maximum 48h before start of treatment dose, in the EoT visit and in the EoS visit. The same method should be used throughout the study for each patient, and preferably performed and assessed by the same assessor.

Single 12-lead ECGs will be obtained as outlined in the schedule of activities using an ECG machine that automatically calculates the heart rate and measures RR interval, QRS interval, QT interval, and QT interval corrected through use of Fridericia's formula (QTcF)/QT interval, PR duration.

Lead placement should be as consistent as possible. ECG recordings must be performed after the participant has been resting in a supine position. All ECGs are to be obtained prior to other medical procedures scheduled at that same time (e.g., vital sign measurements, blood draws). Circumstances that may induce changes in heart rate, including environmental distractions (e.g., television, radio, conversation), should be avoided during the pre-ECG resting period and during ECG recording.

For safety monitoring purposes, the investigator must review all ECG reports. Copies of ECG tracings (paper or digital) will be kept as part of the participant's permanent study file at the site. Any morphologic waveform changes or other ECG abnormalities must be documented on the eCRF. ECG measurement may be performed by an MN professional but reviewed and assessed by the investigator.

Any patient who develops clinical signs or symptoms of cardiac failure should undergo a standard 12-lead ECG, LVEF measurement, and cardiac enzyme assessment.

6.5.4 Physical examination

Assessment of primary tumor and regional lymph nodes must be performed by physical examination at screening and prior to administration of study treatment.

A complete physical examination should also include an examination of head, eyes, ears, nose, and throat as well as cardiovascular, dermatological, musculoskeletal, respiratory, digestive, genitourinary, and neurological systems. Changes to abnormalities identified during the baseline period should be recorded at all subsequent physical examinations. New or worsening abnormalities should be recorded as AEs, if applicable.

6.5.5 Vital signs

These will include the measurement of height (only during screening), weight, respiratory rate, heart rate, blood pressure, and body temperature. Abnormal or significant changes in vital signs from baseline should be recorded as AEs, if appropriate.

